## Clinical Investigation Plan

[REDACTED]

### *TactiFlex PAF IDE*

### *Safety and Effectiveness of TactiFlex Ablation Catheter, Sensor Enabled (TactiFlex SE) for the Treatment of Drug Refractory, Symptomatic, Paroxysmal Atrial Fibrillation*

Version Number

[REDACTED]

Date

May 29, 2020

Planned Number of Sites and Region(s)

Up to 40 sites Worldwide

Clinical Investigation Type

Prospective, non-randomized multi-center clinical investigation. Design includes a main study and a separate substudy. Subjects in the main study are to be treated using the full range of ablation power settings in the IFU. Subjects in the substudy are to be treated in the upper end of the recommended ablation power settings (40-50 Watts).

Sponsor

Abbott

[REDACTED]

CIP Author of Current Version

[REDACTED]

CRD Number

[REDACTED]

[REDACTED]

[REDACTED]

[REDACTED]

### COMPLIANCE STATEMENT:

This clinical investigation will be conducted in accordance with this Clinical Investigation Plan, the Declaration of Helsinki, applicable Good Clinical Practices and regulations (e.g., US 21 CFR Part 50, 21 CFR Part 56, 21 CFR Part 812 and OUS ISO14155:2011) and the appropriate local legislation(s). The most stringent requirements, guidelines or regulations must always be followed. The conduct of the clinical investigation will be approved by the appropriate Institutional Review Board (IRB)/Ethics Committee (EC) of the respective investigational site and by the applicable regulatory authorities (e.g., FDA, PMDA, MHRA, etc.).

## Clinical Investigation Plan

### 1.0 INTRODUCTION

This clinical investigation is intended to demonstrate the safety and effectiveness of the TactiFlex™ Ablation Catheter, Sensor Enabled™ (TactiFlex SE) for treating symptomatic drug-refractory paroxysmal atrial fibrillation. This clinical investigation will be conducted under an investigational device exemption (IDE) and is intended to support market approval of the TactiFlex SE catheter worldwide. Three hundred fifty-five (355) subjects will be enrolled at up to 40 investigational sites worldwide. This clinical investigation is sponsored by Abbott.

This clinical investigation will be conducted in accordance with this CIP. All investigators involved in the conduct of the clinical investigation will be qualified by education, training, or experience to perform their tasks and this training will be documented appropriately.

### 1.1 Background and Rationale

#### 1.1.1 Background

It has been estimated that 33.5 million people have atrial fibrillation (AF) worldwide [1]. AF has a prevalence of approximately 3% in adults aged 20 years or older [2, 3]. Additionally, one in four middle-aged adults in the US and EMEA will develop AF in their lifetime [4, 5].

AF remains a major cause of stroke, heart failure, sudden death, and cardiovascular morbidity. In a meta-analysis of contemporary, well-controlled, randomized clinical trials in AF, the average annual stroke rate is 1.5% with an annualized death rate of 3% in anticoagulated AF patients [6]. A minority of these deaths are related to stroke, while sudden cardiac death and death from progressive heart failure are more frequent, emphasizing the need for interventions beyond anticoagulation [7, 8]. AF is also associated with high rates of hospitalization for AF management, treatment-associated complications, heart failure and myocardial infarction [9, 10]. Patients with AF have significantly reduced quality of life vs. healthy controls, experiencing a variety of symptoms including lethargy, palpitations, dyspnea, chest pain, sleeping difficulties, and mental distress [10-14].

Treatment for AF includes thromboembolic risk management, heart rate control, and heart rhythm control, which includes cardioversion and catheter ablation. The 2014 AHA/ACC/HRS AF Guidelines, 2016 ESC AF Guidelines, and 2017 HRS/EHRA/ECAS/APHRS/SOLAECE Expert Consensus on AF Ablation all provide a Class I recommendation (Level of Evidence: A) for catheter ablation to maintain sinus rhythm for patients with symptomatic, drug refractory, paroxysmal AF [15-17].

Contact force-sensing ablation catheter systems are a technology that is growing in adoption for AF ablation. These contact force-sensing catheter systems provide catheter operators additional feedback by allowing the operator to know how much force is being applied by the catheter tip on the cardiac tissue.

The TactiCath family of contact force-sensing catheters from Abbott has been studied extensively in human clinical trials [18-22]. The latest TactiCath™ contact force sensing catheter from Abbott is the TactiCath SE ablation catheter, which incorporates a magnetic sensor for tracking with the EnSite Precision Mapping System and utilizes a new handle and shaft to improve catheter handling. The TactiCath SE catheter is being investigated by the TactiSense clinical trial [23].

The flexible-tip (“flex-tip”) family of ablation catheters (Therapy™ CoolFlex™, FlexAbility™, FlexAbility™ SE) from Abbott offers a tip design that is significantly different from the rigid-tip TactiCath family. While

## Clinical Investigation Plan

both catheter families provide irrigating saline through 4-6 discrete holes at the distal tip, only the flex-tip family provides irrigating saline through an interlocking pattern of kerfs laser-cut into the side of the electrode that is both flexible and porous. The purpose of having the saline irrigated over a more widely distributed area is to produce a more uniform temperature profile, potentially increasing the efficiency of energy transfer [24] and reducing the risk of steam-pops [25]. The Therapy CoolFlex ablation catheter has been studied in humans for the treatment of typical atrial flutter [26] and the entire flex-tip family is indicated for the treatment of typical atrial flutter in the US. Outside of the US, the flex-tip family of catheters is indicated for treating cardiac arrhythmias and is used to treat AF. The safety and effectiveness of flex-tip catheters has been studied for the treatment of paroxysmal AF in a real-world setting through the ABLATOR patient registry [27].

The TactiFlex™ Ablation Catheter, Sensor-Enabled™ (TactiFlex SE) is the next generation design from Abbott, and it has several elements that are similar or identical to the FlexAbility SE and/or TactiCath SE ablation catheters. The contact force sensor, handle (uni- or bi-directional) and shaft are like TactiCath SE. Meanwhile, the porous flex-tip ablation electrode and therapy RF circuit are like FlexAbility SE. Unlike TactiCath SE and FlexAbility SE, TactiFlex SE has a second magnetic sensor that enables the force direction arrow and deflection/direction features in the EnSite Precision cardiac mapping system (v2.5).

### 1.1.2 Rationale for Conducting this Clinical Investigation

The TactiFlex PAF IDE study will be the first time that the TactiFlex SE ablation catheter has been used in humans. The goal of this clinical trial will be to demonstrate the safety and effectiveness of this catheter for the treatment of paroxysmal AF in the worldwide patient population.

## 2.0 CLINICAL INVESTIGATION OVERVIEW

### 2.1 Clinical Investigation Objective

#### 2.1.1 Primary Objective

The primary objective of the TactiFlex PAF IDE clinical trial is to demonstrate that ablation with the TactiFlex™ Ablation Catheter, Sensor-Enabled™ (TactiFlex SE), in conjunction with a compatible RF generator and three-dimensional mapping system, is safe and effective for the treatment of drug refractory, symptomatic paroxysmal atrial fibrillation (PAF) when following standard electrophysiology mapping and radiofrequency (RF) ablation procedures.

#### 2.1.2 Secondary Objectives

The TactiFlex PAF IDE clinical trial has two secondary objectives:

1. To provide supporting data for the safety and effectiveness of using TactiFlex SE at 40-50 Watts in the left atrium as part of an AF ablation procedure.
2. To provide supporting data for the safety and effectiveness of using TactiFlex SE to treat cavo-tricuspid isthmus (CTI)-dependent (or “typical”) atrial flutter (AFL) through the ablation of the CTI in the right atrium. This data may be used to support an expanded indication for the treatment of CTI-dependent AFL.

## Clinical Investigation Plan

### 2.2 Devices to be Used in the Clinical Investigation

#### 2.2.1 Name of the Device(s) Under Investigation

The components of the ablation system (**Table 1**) to be used in this clinical trial include investigational and commercial devices. In the United States, some commercial devices will be considered investigational when used in this study, while others will be used as commercially indicated. The *Instructions for Use* document for each device and/or *Investigator's Brochure* document for this clinical investigation should be referenced, as appropriate. The list of devices used in the study and their respective model numbers are listed in **Table 1**. In all geographies, the investigational EnSite IDE Display Workstation will be delivered to each clinical site and initially installed by an Abbott employee.

The Ampere RF Generator and TactiSys Quartz Equipment will be obtained by study sites through their usual commercial channels.

#### United States Only

A label indicating each device is considered part of an investigational system for use in the TactiFlex PAF IDE trial will be affixed by Abbott personnel to the Ampere generator and TactiSys Quartz equipment.

#### Outside the United States Only

The models of the Ampere™ RF Generator and Cool Point™ Irrigation pump that are market-released outside of the United States have a different upper power limit (100 Watts) and default irrigation flowrate (17 mL/min) vs. the market-released US models. For this clinical investigation, the recommended irrigation flowrate is 13 mL/min and the power setting must not exceed 50 Watts. Refer to the *Instructions for Use* document for the TactiFlex SE catheter for more information.

**Table 1. Study Devices**

Device Name	Model No. (ZFIN No.) 	Serialized / Lot-Controlled	Manufacturer	Region	Investigational or Market Released
TactiFlex Ablation Catheter, Sensor Enabled	A-TFSE-DD-CLIN A-TFSE-DF-CLIN A-TFSE-FF-CLIN A-TFSE-FJ-CLIN A-TFSE-JJ-CLIN A-TFSE-D-CLIN A-TFSE-F-CLIN A-TFSE-J-CLIN	Serialized	St. Jude Medical 	WW	Investigational
TactiSys™ Quartz Equipment	PN-004 400	Serialized	St. Jude Medical 	US	Commercial Device – Investigational when used as part of the study
				OUS	Commercial
Ampere™ Generator (Software v1.0.6 or greater)	H700488	Serialized	St. Jude Medical 	US	Commercial Device – Investigational when used as part of the study
	H700489	Serialized	St. Jude Medical 	OUS	Commercial

## Clinical Investigation Plan

Device Name	Model No. (ZFIN No.) 	Serialized / Lot-Controlled	Manufacturer	Region	Investigational or Market Released
TactiSys™ Quartz, TactiFlex™ Ablation Catheter SE RF Cable	TSQ-RF-TF-CBL-CLIN	Serialized	St. Jude Medical 	WW	Investigational
Cool Point™ Irrigation Pump (Software v24 or greater)	IBI-89003	Serialized	Irvine Biomedical, Inc., a St. Jude Medical Company	US	Commercial
	85784	Serialized	Irvine Biomedical, Inc., a St. Jude Medical Company	OUS	Commercial
EnSite™ Precision Cardiac Mapping System	Includes models listed below	See below	See below	WW	See status associated with models listed below
EnSite IDE Display Workstation (Investigational Software Velocity v5.5/Precision v2.5 and associated licensed modules)	ESDWS-CLIN1	Serialized	St. Jude Medical 	WW	Investigational
EnSite Velocity Amplifier	100014514	Serialized	St. Jude Medical 	WW	Commercial
EnSite Precision Surface Electrode Kit	EN0020-P	Lot-Controlled	St. Jude Medical 	WW	Commercial
Other EnSite Accessories	Various	Various	Various	WW	Commercial
EnSite Precision Module, Sensor Enabled	H702470, Includes models listed below	Serialized	St. Jude Medical 	US	Commercial
	H702473, Includes models listed below	Serialized	St. Jude Medical 	OUS	Commercial
EnSite Precision™ Field Frame	H702469	Serialized	St. Jude Medical 	WW	Commercial
EnSite Precision™ Link, Sensor Enabled™	H702475 (ZFINs: 100133139, or 100142361)	Serialized	St. Jude Medical 	WW	Commercial
EnSite Precision™ Patient Reference Sensor	H702492	Lot-Controlled	St. Jude Medical 	WW	Commercial
Other EnSite Precision Module Accessories	Various	Various	Various	WW	Commercial

1. [name]
2. [name]
3. Costa Rica Ltda.
4. If specific ZFIN is required.

### 2.2.2 Intended Indication for Use

The TactiFlex™ Ablation Catheter, Sensor Enabled™ (TactiFlex SE) is indicated for use in cardiac electrophysiological mapping and for the treatment of drug-refractory recurrent symptomatic paroxysmal atrial fibrillation, when used in conjunction with a compatible radiofrequency generator and three-dimensional mapping system.

## Clinical Investigation Plan

### 2.2.3 Description of the Device(s) Under Investigation

#### 2.2.3.1 TactiFlex™ Ablation Catheter, Sensor Enabled™

The TactiFlex™ Ablation Catheter, Sensor Enabled™ (TactiFlex SE) is designed to facilitate electrophysiological mapping of the heart chambers and to transmit RF current to the catheter flexible tip electrode for intracardiac ablation purposes. The catheter is used in conjunction with a RF generator, an irrigation pump, and a dispersive pad (indifferent patch electrode) when ablating. TactiFlex SE is compatible with introducers or sheaths with a minimum diameter of 8.5 F. TactiFlex SE is a sterile, single use catheter with a 7.5 F shaft and an 8 F distal section. It is constructed of thermoplastic elastomer material and noble metal electrodes.

TactiFlex SE has a fiber-optic based contact force sensor and a six degree-of-freedom magnetic sensor for position and orientation. It has a fluid lumen connected to an open-irrigated tip electrode for saline irrigation during the ablation procedure (**Figure 1**). For both uni-directional (**Figure 2**) and bi-directional catheters (**Figure 3**), the tip curvature is manipulated by the control mechanism located on the handle at the catheter's proximal end. To adjust the curve of the distal tip on the uni-directional catheter, the thumb control located on the handle may be pushed or pulled. To adjust the curve of the distal tip on the bi-directional catheter, the actuator may be used to deflect the catheter in either direction. The catheter interfaces with standard recording equipment and a compatible RF generator via the TactiSys Quartz Equipment using the optical connector and the 19-pin electrical connector on the catheter. Connection to EnSite Precision magnetic sensor equipment is made using the 10-pin electrical connector on the catheter. The catheters are available in eight distal curve shapes across the two handle types.

Please refer to the IFU for additional information regarding the device used in this clinical investigation.

### Clinical Investigation Plan

Figure 1. Schematic View of the TactiFlex SE Tip

[figure not shown]

Figure 2. Uni-Directional TactiFlex SE

[figure not shown]

Figure 3. Bi-Directional TactiFlex SE

## Clinical Investigation Plan

### 2.2.3.2 EnSite™ IDE Display Workstation

An investigational version of the EnSite Precision Cardiac Mapping System will be used for this clinical study. This investigational software was created from the base EnSite Velocity v5.2.1 / Ensite Precision v2.2 commercial software (K172396), with the following changes:

[REDACTED]

The investigational software will be deployed through the EnSite IDE Display Workstation (Model ESDWS-Clin1).

[REDACTED]

[REDACTED]

Please refer to the IFU for additional information regarding the device used in this clinical investigation.

### 2.2.3.3 TactiSys™ Quartz, TactiFlex™ Ablation Catheter SE RF Cable

The TactiSys™ Quartz, TactiFlex™ Ablation Catheter SE RF Cable (TactiFlex™ RF Cable, TSQ-RF-TF-CBL-CLIN) is an investigational cable that will be used to connect the TactiSys™ Quartz Equipment to the Ampere™ Generator. The Ampere™ Generator is responsible for generating RF energy to transmit to the TactiFlex™ SE catheter. The TactiSys™ Quartz Equipment is responsible for calculating the contact force from the fiber-optic based sensor and is directly connected to the TactiFlex™ SE catheter through the optical connector and the 19-pin electrical connector on the catheter. The Ampere™ Generator transmits RF current to a contact force catheter through the TactiSys™ Quartz equipment via a RF cable. The current contact force catheters (TactiCath SE and TactiCath Quartz), have a RF cable that informs Ampere which default ablation parameters to use.

[REDACTED]

[REDACTED]

## Clinical Investigation Plan

### 2.2.4 Summary of Preclinical Studies

A summary of the preclinical studies for the investigational devices may be found in the Investigator's Brochure (OUS) or in the Report of Prior Investigations (US).

### 2.2.5 Device Handling

Sponsor requires all investigational products to be stored according to the labeling and *Instructions for Use* in a secure area to prevent unauthorized access or use. This applies to the following devices Worldwide:

1. EnSite IDE Display Workstation
2. TactiFlex SE catheters
3. RF cables (Model TSQ-RF-TF-CBL-CLIN)

The market-released TactiSys Quartz Equipment and Ampere generator can be stored per standard practice at each hospital.

## 3.0 CLINICAL INVESTIGATION DESIGN

This is a prospective, non-randomized, multi-center pivotal clinical trial to evaluate the safety and effectiveness of ablation with the TactiFlex SE catheter for the treatment of PAF compared to pre-determined performance goals. The study design includes a substudy to assure that there will be at least 50 subjects ablated at the high-end of the ablation power setting recommendations in the investigational *Instructions for Use* document. Subjects in the HSP (High Standard Power) substudy are to undergo the same study procedures as subjects in the main study, except that ablation power settings of 40-50 Watts are to be used in the left atrium, unless there is a medical reason to use a lower power. Operators will be assigned to either the main study or the HSP substudy based on the ablation power settings they currently use in their standard practice. Subjects will be enrolled in either the main study or the substudy at the point of consent based on the operator that is expected to perform their ablation procedure. After the substudy has enrolled 50 subjects, or if the Sponsor has provided written permission, HSP operators may transition to the main study and treat main study subjects. No site may enroll more than 10 subjects (20%) in the HSP substudy without Sponsor pre-approval and at least 25 HSP substudy subjects (50%) must be from the United States.

Up to 40 sites worldwide will participate in the TactiFlex PAF IDE clinical study. The TactiFlex IDE Clinical Study will enroll a total of 355 subjects. Fifty (50) subjects will be enrolled in the HSP Substudy and 305 subjects will be enrolled in the Main Study. No center may contribute more than 20% (N=61) of the total number of enrollments in the main study without Sponsor pre-approval. At least 50% (N=153) of the subjects will be from the US.

Subjects will be followed for 12-months after their initial ablation procedure. The primary and secondary endpoints will be evaluated when all subjects have completed their 12-month follow-up visit.

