## 4.3 HSP Substudy Endpoints

The endpoints for the HSP substudy will be defined the same as the Primary and Secondary Endpoints for the main study. Results will be reported descriptively using summary statistics. No pre-specified hypothesis testing will be performed.

The following as-treated analyses will be performed using the Primary and Secondary Endpoint results from main study and HSP substudy subjects.

1. Results will be summarized separately for subjects that have time-averaged power settings of  $\geq 40$  Watts vs.  $< 40$  Watts in the left atrium.

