### 6.3.4 Ablation Parameters

The procedure should be performed according to the TactiFlex SE investigational *Instructions for Use* document using the recommended ablation parameters as noted in the document.

**Note:** Investigators treating HSP substudy subjects are required to use ablation power settings of 40-50 Watts in the left atrium, unless medically justified. Investigators not treating HSP substudy Subjects are to follow the ablation power recommendations provided in the investigational *Instructions for Use* document.

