1.4.4 HSP Substudy Endpoints

The endpoints for the HSP substudy will be defined the same as the Primary and Secondary Endpoints for the main study. Results will be reported descriptively using summary statistics. No pre-specified hypothesis testing will be performed.

The following as-treated analyses will be performed analyzing the Primary and Secondary Endpoints and the Additional Data described above for main study and HSP substudy subjects (with the exception of Additional Data items 9-12).

1. Results will be summarized separately for subjects that have time-averaged power settings of ≥ 40 Watts vs. < 40 Watts in the left atrium.
2. Results will be summarized separately for subjects that have $\geq 50\%$ vs. $< 50\%$ of lesions in the left atrium with power settings ≥ 40 Watts.
3. Results will be summarized separately for subjects that have $\geq 25\%$ vs. $< 25\%$ of lesions in the left atrium with power settings ≥ 40 Watts.

The rationale for the HSP Substudy is provided in **Appendix I**.

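### The as-treated power groups can take in power chosen after a problem during ablation, which could make 40-50 W look safer than it is

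*Protocol*

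**What the plan says.** The first secondary objective is "To provide supporting data for the safety and effectiveness of using TactiFlex SE at 40-50 Watts in the left atrium" during an AF ablation (Protocol 2.1.2). Subjects join the 50-subject HSP substudy or the 305-subject main study at consent, according to the operator expected to treat them. Protocol 3.0 states that in the substudy settings of 40-50 W "are to be used in the left atrium, unless there is a medical reason to use a lower power". Protocol 6.3.4 repeats the exception: HSP investigators "are required to use ablation power settings of 40-50 Watts in the left atrium, unless medically justified".

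Two kinds of summary follow. HSP results are reported descriptively for the substudy as enrolled, without hypothesis tests. Protocol 4.3 then adds: "The following as-treated analyses will be performed using the Primary and Secondary Endpoint results from main study and HSP substudy subjects". SAP 1.4.4 defines three such groupings. The first reads "Results will be summarized separately for subjects that have time-averaged power settings of ≥ 40 Watts vs. < 40 Watts in the left atrium". The other two split subjects at 50% and at 25% on the share "of lesions in the left atrium with power settings" of at least 40 W.

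The visible text does not say whether power used after a complication or warning sign counts, or how power from a repeat procedure is handled. SAP 2.1.6 (As-Treated population) and SAP Appendix I (HSP rationale) are redacted.

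**The concern.** The groups are formed from what happened during treatment, while the allowed reason for lowering power is medical and so may be linked to the safety outcome. If a problem arises at 40-50 W and the operator completes the left-atrial ablation at a lower setting, the later applications pull down both the time-averaged power and the share of lesions at 40 W or more. The subject may then be counted as low power, with any resulting safety event charged to that group. Group membership would depend partly on the outcome or its precursor, and the high-power group would be selected for subjects who tolerated high power.

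At stake is how far the as-treated safety tables can be trusted for the first secondary objective. They matter because they are the visible tables that add main-study subjects treated at high power to the 50 HSP subjects.

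**Working it through.** The plan states no rate, size or precision for the as-treated comparison, so there is no figure of its own to reproduce.

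**1. When does a subject change group?** Let H be the starting setting, L the lowered setting and f the share of left-atrial RF time at H. Time-averaged power is f·H + (1 − f)·L. It stays at 40 W or above only if f ≥ (40 − L)/(H − L). The 40 W cut is from SAP 1.4.4; the H and L values are assumptions.

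| H | L = 25 W | L = 30 W | L = 35 W |
|---|---|---|---|
| 40 W | 15/15 = 100% | 10/10 = 100% | 5/5 = 100% |
| 45 W | 15/20 = 75% | 10/15 = 66.7% | 5/10 = 50% |
| 50 W | 15/25 = 60% | 10/20 = 50% | 5/15 = 33.3% |

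A subject started at 40 W moves after any time at a lower setting. One lowered from 50 W to 30 W moves if less than half the RF time was at 50 W.

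Example with lesions of equal duration: 30% at 50 W and 70% at 30 W gives 0.3 × 50 + 0.7 × 30 = 36 W. The subject is below 40 W on the time average and below the 50% lesion cut, but above the 25% cut. The 25% grouping is the hardest to leave.

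**2. What does one moved event do?** A high-power group with k events in n subjects goes from k/n to (k − 1)/(n − 1). The event counts are assumptions; the limits are exact Clopper-Pearson, the interval named in SAP 2.2.2.

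- None moved: 3/50 = 6.0% (upper 95% limit 16.5%).
- One moved: 2/49 = 4.1% (14.0%).
- Two moved: 1/48 = 2.1% (11.1%).

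The drop from one move is (1 − k/n)/(n − 1): here 0.94/49 = 1.9 percentage points. If main-study subjects doubled the group at the same rate, one move would give 5/99 = 5.1% instead of 6/100 = 6.0%, a drop of 0.94/99 = 0.9 points.

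**3. What if the true rates are equal?** Take the enrolled sizes, 50 and 305, as the groups before any move, a true rate r in both, and a share q of the high-power events moved. The high-power rate becomes 50r(1 − q)/(50 − 50rq) and the low-power rate (305r + 50rq)/(305 + 50rq). The values of r and q are assumptions, except that 12.9% is the safety performance goal in Protocol 4.1.1.

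| True rate | q = 10% | q = 25% | q = 50% |
|---|---|---|---|
| 5% | 4.5% vs 5.1% | 3.8% vs 5.2% | 2.6% vs 5.4% |
| 8% | 7.3% vs 8.1% | 6.1% vs 8.3% | 4.2% vs 8.6% |
| 12.9% | 11.8% vs 13.1% | 10.0% vs 13.4% | 6.9% vs 13.8% |

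Each cell is high-power vs low-power. The apparent difference runs from 0.6 points to 6.9 points.

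**4. Which events can move a subject?** Only a complication or warning sign during left-atrial ablation that is followed by more left-atrial ablation at lower power. A complication that ends the procedure, or one found afterwards, leaves the power record unchanged. Right-atrial CTI lesions do not count in any of the three groupings.

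**5. What about repeat procedures?** Protocol 6.6.4 allows the study catheter for a repeat on days 31-80 and not from day 81. Protocol 4.1.2 does not count recurrence up to day 90 as failure. The permitted repeat thus comes before any recurrence that counts. Its power can follow the outcome in two cases only: the single-procedure endpoint, where a repeat left-atrial ablation is itself a failure (Protocol 4.2.2), and safety events of the initial procedure.

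**The case against.** The strongest reply is that the plan already contains an unaffected comparison. HSP membership is fixed at consent, and the HSP results and additional data are reported by assignment. The as-treated tables are descriptive, and the three cut-offs act as a partial check on one another: the 36 W subject above stays in the high-power group at the 25% cut. All of this stands. It limits the consequence but does not remove the mechanism. The assigned summary covers only 50 subjects, and nothing visible requires it to be shown beside the as-treated tables.

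It can also be said that the direction is not shown. The medical reasons are not defined and could be known before ablation. For a rise in oesophageal temperature, Protocol 6.3.3 recommends stopping energy; it does not describe continuing at lower power. Many safety components can surface after ablation and cannot alter the power used. This also stands, so the claim is only that the tables could favour high power.

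The redactions matter too. A reader might infer that no cut-off rule exists. The documents do not support that, because SAP 2.1.6 or Appendix I may contain one.

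Finally, starting power has its own weakness: one application at 50 W followed by planned applications at 30 W would count as high power. It therefore belongs beside the delivered-power groupings, not in their place.

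**Conclusion.** The concern holds for the as-treated tables, and chiefly for the safety endpoint. As visible, the rule lets power chosen after a problem during ablation decide the group, which could lower the apparent event rate at 40-50 W. The size cannot be derived from the documents. It depends on how many events or warning signs arise during ablation, how often ablation then continues at lower power, and how many main-study subjects enlarge the high-power group. Under the assumed 3 events in 50, one move is worth about 2 points. If only a tenth of events move at a true rate of 5%, the high-power figure shifts by half a point.

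Two stronger readings are not supported. A reader might infer that re-ablation makes the primary effectiveness grouping depend on recurrence; the day-80 limit on repeats and the 90-day blanking period rule that out, and the same holds for recurrence in the AAD-free and symptomatic endpoints. A reader might also infer that trial success is affected; it is not, because no hypothesis test uses these groups.

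**What to change.** First check whether the redacted As-Treated section already has a suitable rule. If not, amend SAP 1.4.4 and Protocol 4.3 as follows:

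- For the safety endpoint, add a grouping by left-atrial power setting at the start of ablation, with the number of first applications defined. Show it beside the three delivered-power groupings and the HSP result by assignment.
- Attribute each safety event to the power of the procedure it followed, initial or repeat. Using the initial procedure alone would charge repeat-procedure events to power not used that day. State the rule for the three components followed to 12 months when a subject has had both procedures.
- Base the grouping for the single-procedure endpoint on the initial procedure.
- List every HSP subject, and every other subject who started at 40 W or more, who was lowered below 40 W, with reason, timing and safety outcome.

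The cost is one extra table and one listing. The power data come from the EnSite recordings and Ampere logs already collected (Protocol 6.3.6 and Table 4). For repeats, Protocol 6.6.4 names only the EnSite recording, while Table 4 note 2 asks for the same information as at the initial procedure, so collection of the Ampere log should be confirmed. The 40-50 W safety figures may look slightly less favourable. No change to the power rule itself is proposed.
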